6.2. Inclusion and exclusion criteria specific to CRAFT-RCT

Inclusion criteria:

- Pregnant women between 14⁺⁰ and 23⁺⁶ weeks gestation with a history of FDSC.
- Short cervix (≤ 25 mm) on transvaginal ultrasound scan.

Exclusion criteria:

- Women with persistent fresh vaginal bleeding evident on speculum examination.
- Women with visible fetal membranes evident on speculum examination or open cervix on ultrasound scan.
- Women with severe abdominal pain/evidence of sepsis (as judged by attending clinician).
- Known significant congenital or structural or chromosomal fetal abnormality.
- Suspected or proven rupture of the fetal membranes at the time of recruitment.

6.3. Inclusion and exclusion criteria specific to CRAFT-IMG

Inclusion criteria:

- Pregnant women between 14⁺⁰ and 23⁺⁶ weeks gestation with a history of FDCS.

Exclusion criteria:

- Contraindications to MRI, e.g. claustrophobia, BMI >40 kg/m² (due to technical limitations of scanner) or a women with a non-MRI compatible metallic implant.

7. Study procedures

7.1. Identification of participants

CRAFT-OBS

We will recruit pregnant women who are booked for their delivery at participating centres who provide written informed consent to participate in the study and who meet the study eligibility criteria.

Women who have previously had an emergency caesarean in labour will be identified through their booking appointment or scan appointments by the direct care midwife, doctor, sonographer and approached with information about this observational study. Clinical midwives, doctors or sonographers will highlight eligible women to the research team. The research team will then be able to discuss the research with patients if they are eligible at the time of their first trimester or second trimester scan.

CRAFT-RCT

Women participating in CRAFT-OBS will be eligible for CRAFT-RCT if they are found to have a cervix ≤ 25 mm prior to 23⁺⁶ weeks gestation with a history of FDCS. Women with a previous full dilatation caesarean section will be identified by a member of the direct care team and referred for cervical surveillance as per new guidance (1,2). The research team will check relevant hospital records when patients are consented in order to confirm a previous full dilatation caesarean section occurred. If these records are not available for review the patients will be excluded. Eligible women will be informed about the trial by a doctor, sonographer or midwife if their transvaginal ultrasound confirms a short cervix (≤ 25 mm). Members of the research team

Study Protocol: **Cerclage After Full-dilatation caesarean-section**

IRAS ID:261294

REC: REC 19/LO/1270

Version 2.0

Date: 10.09.19

(midwives, doctors and scanning practitioners) can then discuss the research further and consent women.

- If a woman is randomised to a cervical cerclage, the procedure needs to take place within 7 days of diagnosis of cervical shortening and removed around 37 weeks gestation. She will also have regular scan surveillance in accordance with local protocols. Rescue cerclage can be offered in cases of cervical opening with exposed membranes as per local guidelines. Targeted admission for bedrest and steroids can also be offered as per clinician practice and local protocols.
- If a woman is randomised to the standard care arm; she will have regular surveillance scans and clinic visits in accordance with local protocols and clinician practice. Rescue cerclage can be offered in cases of cervical opening with exposed membranes as per local guidelines. Targeted admission for bedrest and steroids can also be offered as per clinician experience and local protocols.

Concomitant medication during RCT

Participants are permitted to use any concomitant medication or treatment except progesterone alongside the trial management. This will be recorded at every visit on the RedCap database. Any other medication or treatment that would form normal clinical management for these women at risk of preterm labour i.e. antibiotics, corticosteroids, tocolytics etc. will be permitted according to the local hospital guidelines and clinician preference.

CRAFT-IMG

Participants will be identified from CRAFT-OBS (30 women with history of FDCS and cervical length >25mm) and CRAFT-RCT (30 women with FDCS and short cervix (\leq 25mm) by their direct care team. Interested women will be directed to have more information from the research team as well as confirmation of informed consent. 15 women from CRAFT-RCT will have been randomised to cerclage and the other 15 to standard management. Only women recruited at St Thomas' Hospital and UCLH will be eligible for this part of the CRAFT project. Doctors, sonographers or midwives in the research team will be recruiting patients to this sub-study.

All MRI scans will be performed at St Thomas' Hospital, and advanced protocol transvaginal ultrasound scans will be performed at both UCLH and St Thomas' Hospital. Repeat imaging will

be undertaken at regular intervals up to a maximum of 3 MRIs and 3 TVUS depending on patient availability in order to assess changes in the cervical tissue using the two imaging modalities.

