Primary objective	
 1. CRAFT-OBS: To assess the risk of preterm birth or late miscarriage in women following an in labour caesarean section 2. CRAFT-RCT: To assess if cervical cerclage reduces preterm birth in pregnant women with a short cervix following a previous in labour caesarean section 3. CRAFT-IMG: To assess if alterations in MRI parameters or ultrasound characteristics occurs in women who undergo a late miscarriage or preterm birth following an in labour caesarean section.
Trial Design	Prospective observational study, nested randomised controlled trial and imaging sub-study in a selected cohort
Endpoints	Incidence of preterm birth at < 34 weeks gestation
Sample Size	CRAFT-OBS: 2200 women, CRAFT-RCT: 1000 women, CRAFT-IMP: 60 women

Study Protocol: **Cerclage After Full-dilatation caesarean-section**

IRAS ID:261294

REC: REC 19/LO/1270

Version 2.0

Date: 10.09.19

Summary of eligibility criteria	CRAFT-OBS: pregnant women 14 ⁺⁰ -23 ⁺⁶ week with a previous history of caesarean section in labour. CRAFT-RCT: pregnant women with a previous history of caesarean section carried out at full dilatation and a short cervix ($\leq 25\text{mm}$) in current pregnancy. CRAFT-IMG: pregnant women with a previous history of caesarean section carried out at full dilatation (30 women with cervix $>25\text{mm}$; 30 CRAFT-RCT participants).
Maximum duration of treatment of participant	Until delivery or removal of cerclage at 37 weeks gestation
Version and date of final protocol	Version 2.0 (10/09/19)
Version and date of protocol amendments	To be inserted

[figure not shown]

Figure 1: Flow of participants through CRAFT project

STUDY SYNOPSIS.....	4
LAY SUMMARY.....	8
PROFESSIONAL SUMMARY	8
GLOSSARY OF TERMS	11
1. Introduction.....	12
1.1. Background.....	12
1.2. Rationale for study.....	13
Study aims and objectives	15
2.	
2.1. Aims.....	15
2.2. Study objectives	15
2.2.1. CRAFT-OBS: a study of risk and management in women with a history of CS in labour	15
2.2.2. CRAFT-RCT: a trial of USS indicated cerclage in women with history of FDCS	16
2.2.3. CRAFT-IMG: a sub-study evaluating imaging methods for assessing risk and management of women with a history of FDCS.....	16
3. Study Design	16
3.1. CRAFT-OBS.....	16
3.2. CRAFT-RCT	16
3.3. CRAFT-IMG	17
3.4. Expected study duration	17
4. Study Endpoints	17
4.1. CRAFT-OBS.....	17
4.2. CRAFT-RCT	18
4.3. CRAFT-IMG	18
5. Sample size and power calculation	19

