2.2. Study objectives

2.2.1. CRAFT-OBS: a study of risk and management in women with a history of CS in labour

- i. Determine the incidence of LM and PTB (prior to 37 weeks) in women with previous CS in labour stratified by cervical dilatation.

- ii. If ultrasound measured cervical length and quantitative fibronectin are carried out, this data will be collated and help evaluate the ability of these tests to determine risk of preterm birth in women with a history of in labour caesarean.

2.2.2. CRAFT-RCT: a trial of USS indicated cerclage in women with history of FDCS

- i. Determine if an ultrasound-indicated cervical cerclage is effective management in women with a history of FDCS and cervical shortening (<25 mm) in preventing LM or PTB <34 weeks gestation. Evaluate the impact of intervention on short-term fetal and neonatal outcomes, assessed as a composite of fetal and perinatal death and major morbidity.
- ii. Assess the impact of both management strategies (i.e. cerclage and observation) on health economic outcomes for mother and infant in terms of number of nights in hospital; cost data to hospital discharge/28 days post delivery.

2.2.3. CRAFT-IMG: a sub-study evaluating imaging methods for assessing risk and management of women with a history of FDCS

- i. Ascertain whether MRI or ultrasound (or a combination of the two) can accurately predict PTB when abnormalities are detected in the cervix.
- ii. Identify which women are most likely to benefit from intervention.

3. Study Design

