4.1. CRAFT-OBS

Primary endpoint:

- i) Delivery < 37 completed weeks gestation (powered).

Secondary endpoints

- i) Adverse perinatal outcome, defined as a composite outcome of death (ante-partum/intra-partum stillbirths plus neonatal deaths prior to discharge from neonatal services)
- ii) Delivery <34 weeks gestation.
- iii) Gestation at delivery.
- iv) Late miscarriage (14⁺⁰-23⁺⁶ weeks).
- v) Healthcare use, e.g. appointments, hospital admission, cervical length, cervicovaginal fetal fibronectin levels, interventions.
- vi) Predictive modelling to evaluate the ability of CL and fFN to determine risk of preterm birth <34 and <37 weeks
- vii) Other maternal and fetal morbidities, as per COPOP core outcome set for preterm birth intervention studies(15).

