6.1. Inclusion and exclusion criteria for ALL CRAFT participants

Inclusion criteria:

- Pregnant women under 23⁺⁶ weeks gestation with a history of previous caesarean section in labour.
- Singleton pregnancy.
- Willing and able to give informed consent (with or without interpreter).

Exclusion criteria:

- Under 16 years of age.
- Inability to give informed consent.
- Previous caesarean section carried out before labour.
- Women who have been commenced on management with progesterone, a cerclage or arabin pessary as part of their care or another research study

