7.2. Consent procedure

The study will be verbally explained to potential participants who will be given a written patient information sheet and adequate time for consideration and clarification of any queries. They can take the information home. For CRAFT-OBS and CRAFT-IMG, eligible patients will have until their next appointment to decide on participation and provide informed written consent. For CRAFT-RCT, eligible patients will generally have up to 48 hours to decide on participation, depending on the length of their cervix and urgency of treatment as determined by the attending clinician.

Written consent will be confirmed by an appropriately trained (GCP) clinician or researcher. Three copies of the consent form will be taken (1 for participant, 1 for clinical notes (unless electronic records), 1 for site file). At the time of recruitment, a unique study number will be allocated to the patient. Only one copy of patient identifiable data linked to this number will be recorded on a password protected KCL computer in order that recruits can be contacted and delivery outcomes recorded. The research record will contain minimal identifiers such as initials and date of birth. Keeping initials and date of birth on the research database allows the data to be double-checked against source outcome data, therefore enhancing the reliability of the data.

Consent will be sought to obtain NHS numbers for future tracking of outcomes. NHS numbers (mother and baby) will be collected to aid linkage to these future health records as well as follow up pregnancy and neonatal outcomes for recruits who move away from study sites. NHS numbers will be held separately from main study data and only linked with study ID. Access to this information will be limited to specific study staff. They will also be explicitly consented for use of the study data for future research, collection of additional data on any future pregnancies and whether they would be happy to be contacted about participation in further research studies that may be of interest to them.

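### CRAFT-OBS women can enter well after 14+0 weeks, so a simple proportion of enrolled women understates late miscarriage; section 8 should use a delayed-entry analysis

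*Combined protocol and SAP*

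**What the plan says.** **Objective.** The synopsis gives the CRAFT-OBS primary objective as "To assess the risk of preterm birth or late miscarriage in women following an in labour caesarean section". Objective 2.2.1(i) is to "Determine the incidence of LM and PTB (prior to 37 weeks) in women with previous CS in labour stratified by cervical dilatation". Section 4.1 makes delivery before 37 weeks the powered primary endpoint, with no lower gestational limit. It lists late miscarriage, from 14+0 to 23+6 weeks, as secondary endpoint (iv).

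**Entry.** Section 6.1 admits "Pregnant women under 23⁺⁶ weeks gestation with a history of previous caesarean section in labour", with no lower limit. The synopsis gives the CRAFT-OBS window as 14+0 to 23+6, and the two have not been reconciled. Under section 7.1 the research team may approach women "if they are eligible at the time of their first trimester or second trimester scan". Section 7.2 adds that "eligible patients will have until their next appointment to decide on participation", so consent can fall later than the scan. Section 6.1 also excludes "Women who have been commenced on management with progesterone, a cerclage or arabin pessary as part of their care or another research study".

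**Analysis.** For CRAFT-OBS, section 8 relies on observed pregnancy outcomes, reported as odds ratios and risk differences, and names delivery before 34 and 37 weeks. It does not mention gestation at entry, delayed entry or a landmark, and it gives no denominator for late miscarriage.

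**The concern.** Being enrolled at a given gestation means that the pregnancy has survived to that gestation. Losses between 14+0 and a woman's consent never reach the dataset, whereas the women who passed through that interval safely do. Dividing observed late miscarriages by all enrolled women credits late entrants with weeks in which they could not have had the event.

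The lay summary says that the suspected harm falls mainly before 28 weeks and causes many late miscarriages, so part of the window of interest is the part lost. The result at stake is the late-miscarriage estimate by dilatation group. If the groups also enter at different gestations, the comparison between them is distorted as well.

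**Working it through.** **The plan's own figure.** Section 5 asks for 2200 women to estimate a 15% rate to 10% relative accuracy (±1.5 points). Assuming a 95% interval, n = 1.96² × 0.15 × 0.85 / 0.015² = 2177, which agrees with 2200. At n = 2200 the half-width is 1.49 points (13.5% to 16.5%; the upper limit of 15.6% printed in section 5 does not match this). The ±1.5 points is the yardstick for the primary endpoint below.

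**Assumptions, none of them given in the documents.** The late-miscarriage hazard is constant over 14 to 24 weeks with cumulative risk R (2% and 5% tried). A share f of women pregnant at 14+0 would enrol at week e if still pregnant; the others are enrolled by 14+0. Entry time is unrelated to risk.

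**Formulas.**
- Survival to entry: S(e) = (1 − R)^((e − 14)/10)
- Simple incidence = [(1 − f)R + f(S(e) − (1 − R))] / [(1 − f) + f·S(e)]

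**Example: R = 5%, e = 20, f = 50%.** S(20) = 0.95^0.6 = 0.9697. The numerator is 0.025 + 0.5 × 0.0197 = 0.0348 and the denominator is 0.5 + 0.5 × 0.9697 = 0.9848. The simple incidence is 3.54% against a true 5%, about 0.70. As a quick check, the share missed is roughly f × (20 − 14)/10 = 0.30.

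**Range at e = 20.**

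| Late entrants f | R = 5% | R = 2% | Approximate fraction of truth |
|---|---|---|---|
| 25% | 4.27% | 1.70% | 0.85 |
| 50% | 3.54% | 1.41% | 0.70 |
| 75% | 2.79% | 1.11% | 0.55 |
| 100% | 2.03% | 0.80% | 0.40 |

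With f = 50%, the fraction is about 0.80 for entry at 18 weeks and 0.60 for entry at 22 weeks.

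**Does delayed entry recover the truth?** A simulation with R = 5%, f = 50% and e = 20 gave a simple incidence of 3.56% and a delayed-entry Kaplan-Meier estimate of 5.01%.

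**Group comparison.** Take true risks of 5% (full dilatation) and 2% (4 to 9 cm), a true ratio of 2.5, with late entry at 20 weeks:
- 50% late in both groups: 3.54/1.41, ratio 2.52
- 25% late v 75% late: 4.27/1.11, ratio 3.86
- 75% late v 25% late: 2.79/1.70, ratio 1.64

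**Primary endpoint, if the 15% includes late miscarriages.** Add 0.15 − R to the numerator. With R = 2% the observed rate is 14.5% (f = 50%) or 14.0% (f = 100%). With R = 5% it is 13.7% or 12.3%.

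**Births at 24 to 37 weeks.** All entry is before 24 weeks, so none is missed. In the worked example the denominator shrinks to 0.985, so their observed proportion rises by about 1.5% in relative terms (1/0.985).

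**The case against.** **Does section 8 commit to the wrong denominator?** Not explicitly. It specifies no late-miscarriage analysis and no time origin, and gestation at delivery is itself an endpoint in section 4.1. The criticism is that the plan is silent, and that odds ratios and risk differences on observed outcomes would carry the bias by default.

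**Is the whole preterm birth estimate biased downward?** A reader might infer this, but the documents do not support it. Only losses before consent are missed, and consent must come before 23+6. Delivery before 37 weeks is affected only through any late miscarriages it includes. In the scenarios above the shortfall stays within ±1.5 points, except when R is 5% and every woman enters at 20 weeks.

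**Do full-dilatation women enter earlier, inflating their relative risk?** This too is tempting, because they are referred for cervical surveillance. But nothing says that the referral is early. Section 7.1 gives one identification route, at booking or scan appointments, for all women with a previous caesarean in labour, and section 7.3 describes referral of women already participating. Since CRAFT-RCT candidates come from CRAFT-OBS, some full-dilatation women could equally be enrolled late, through surveillance. The direction is unknown.

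**Is delayed entry a complete cure?** No. It assumes that entry time is unrelated to risk within each group. Women entering through surveillance, and the exclusion of women already treated, may violate this. Restricting to women enrolled by 14+0 is not a safe fallback either: if the synopsis window applies, that set may be almost empty. These points stand and shape the fix.

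**Conclusion.** The point holds for late miscarriage and is a cheap improvement to the analysis, not a flaw that calls for redesign. If some women consent after 14+0, there is a risk of loss before they do, and entry time is unrelated to risk, the simple proportion is too low. Its size cannot be derived from the documents. Under a constant hazard with late entry at 20 weeks it is about 0.85, 0.70 and 0.40 of the truth for 25%, 50% and 100% late entry. The effect on delivery before 37 weeks is smaller and depends on whether that endpoint includes late miscarriages.

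Bias between dilatation groups is a possibility only: under the assumed risks, a true ratio of 2.5 could appear as about 3.9 or about 1.6, depending on which group enters later.

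**What to change.** In section 8, under CRAFT-OBS:

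1. Estimate the cumulative incidence of loss or delivery to 24, 34 and 37 weeks by dilatation group with delayed entry, each woman joining the risk set at her gestation at consent. Confirm that the consent date is recorded in the study database; section 7.3 already provides ultrasound dating, and gestation at delivery is an endpoint.
2. As sensitivity, report risk from a stated landmark gestation by which enough women are enrolled (for example 16+0), among those enrolled and still pregnant then, instead of relying only on women enrolled by 14+0.
3. State the assumption that entry time is unrelated to risk within dilatation group, and note that entry through surveillance and the exclusion of women already treated may violate it.
4. Reconcile the entry windows in the synopsis (14+0 to 23+6) and section 6.1 (under 23+6), and say whether delivery before 37 weeks includes late miscarriages.

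The cost is analysis wording and a check on one data item. The downside is somewhat wider intervals at early gestations, where the risk set is small.

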7.2. Consent procedure

The study will be verbally explained to potential participants who will be given a written patient information sheet and adequate time for consideration and clarification of any queries. They can take the information home. For CRAFT-OBS and CRAFT-IMG, eligible patients will have until their next appointment to decide on participation and provide informed written consent. For CRAFT-RCT, eligible patients will generally have up to 48 hours to decide on participation, depending on the length of their cervix and urgency of treatment as determined by the attending clinician.

Written consent will be confirmed by an appropriately trained (GCP) clinician or researcher. Three copies of the consent form will be taken (1 for participant, 1 for clinical notes (unless electronic records), 1 for site file). At the time of recruitment, a unique study number will be allocated to the patient. Only one copy of patient identifiable data linked to this number will be recorded on a password protected KCL computer in order that recruits can be contacted and delivery outcomes recorded. The research record will contain minimal identifiers such as initials and date of birth. Keeping initials and date of birth on the research database allows the data to be double-checked against source outcome data, therefore enhancing the reliability of the data.

Consent will be sought to obtain NHS numbers for future tracking of outcomes. NHS numbers (mother and baby) will be collected to aid linkage to these future health records as well as follow up pregnancy and neonatal outcomes for recruits who move away from study sites. NHS numbers will be held separately from main study data and only linked with study ID. Access to this information will be limited to specific study staff. They will also be explicitly consented for use of the study data for future research, collection of additional data on any future pregnancies and whether they would be happy to be contacted about participation in further research studies that may be of interest to them.

7.3. Data Collection

Following consent, data on the participant's demographic characteristics, risk factors, medical and obstetric history will be documented and entered onto the study specific database. This will include current and previous monitoring procedures and/or pregnancy interventions (e.g. cervical length measurements and cerclage). Cervical length will be measured with transvaginal

Study Protocol: **Cerclage After Full-dilatation caesarean-section**

IRAS ID:261294

REC: REC 19/LO/1270

Version 2.0

Date: 10.09.19

ultrasound in accordance with local protocols, measurements will be taken in triplicate and the shortest measurement used. Their pregnancy and neonatal outcomes will be collected from NHS patient records postnatally.

Participants with a history of FDCS will be referred to a preterm surveillance clinic where they will be invited for cervical length assessment (with or without other tests, such as fetal fibronectin) from 14+0 to 23+6 weeks gestation. Cervical length will be measured with transvaginal ultrasound in accordance with local protocols, measurements will be taken in triplicate and the shortest measurement used. If their cervical length is, or becomes ≤ 25 mm during this period they will be offered the opportunity to participate in CRAFT-RCT. Further explanation and a separate information sheet will be provided and additional consent form will be completed and stored as those for the main study. If the participant is unwilling to participate in this randomised controlled trial she will continue to be monitored and cared for as per local protocol/clinicians' experience, and continue in the observation arm of CRAFT study. Outcome data will be collected after the birth of her baby. Women who provide written informed consent will be randomised to either cervical cerclage or standard care.

Sixty participants, recruited at St Thomas' and UCLH, will be invited to have additional imaging tests for the sub-study, CRAFT-IMG. They will be given additional information and asked to sign another consent form, which will be stored as described above. These additional tests will involve serial transvaginal ultrasound measurements of cervical length and macro/microstructural changes as per [name] protocol and MRI scans of macro/microstructural cervical change.

Serial MRI scans will be performed on a 3-Tesla MRI scanner at St Thomas' Hospital. Conventional imaging will include high resolution T1 and T2 weighted images as well as diffusion datasets. The first advanced protocol transvaginal ultrasound and MRI will occur at any time from 20 weeks gestation. Where delivery has not occurred, further imaging will be offered (up to a maximum of 3 MRI and 3 of these transvaginal ultrasound scans).

Outcome data: All participants' data will be collated up until postnatal discharge. Neonates will be followed up until discharge or 28 days (whichever is sooner). Prompts on the database will alert the research midwife/assistant when each trial participant reaches her delivery date. Birth registers and in-patient records will be used to track hospital admissions and pregnancy outcomes. Outcome data (medical and economic) will be collected by review of NHS Maternity and medical records. If information is unavailable, e.g. if the delivery occurred elsewhere, the patient, patient's GP or other hospital will be contacted. Gestational age will be calculated using Study Protocol: **Cerclage After Full-dilatation caesarean-section**

IRAS ID:261294

REC: REC 19/LO/1270

Version 2.0

Date: 10.09.19

ultrasound estimated date of delivery predicted at the 12-15 week ultrasound scan. The primary and secondary outcome data will be collected from hospital records after discharge from neonatal care.

Source data and documents will be accessible by the research team only and any paper records will be stored in a locked cabinet in the Principal Investigators' offices. Electronic versions of these source documents are stored on Trust computers only and behind the NHS firewall. The study may be subject to inspection and audit by King's College London and Guy's and St Thomas' NHS Foundation Trust under their remit as sponsor and co-sponsor respectively, and other regulatory bodies to ensure adherence to GCP and the NHS Research Governance Framework for Health and Social Care.

The identifiable information obtained as part of this study will be managed in accordance with the General Data Protection Act (2018). The computerised information is protected by a software and hardware barrier, and the records are handled in the same way as hospital records. Data will be stored for 25 years in Trust firewalls/KCL Firewalls in accordance with legal requirements for the storage of maternity records.

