We will screen all pregnant women with a history of caesarean section in labour booked for maternity care at all participating sites with transvaginal ultrasound and quantitative fetal fibronectin (if available) between 14⁺⁰ and 23⁺⁶ weeks with a previous in labour CS. These women will be grouped into:

1. Unknown dilatation at time of CS in labour.
2. Dilated 4cm to 9cm at time of CS in labour.
3. Full dilatation at time of CS in labour.

This part of the project will allow us to:

1. Determine pregnancy outcomes in women who have had previous in-labour CS.
2. Evaluate risk of PTB/LM according to degree of dilatation in previous in-labour CS.

Study Protocol: **Cerclage After Full-dilatation caesarean-section**

IRAS ID:261294

REC: REC 19/LO/1270

Version 2.0

Date: 10.09.19

3. Evaluate the predictive value of quantitative fetal fibronectin in women with previous CS in labour if done by direct care team for clinically indicated reasons at any point
4. Evaluate the predictive value of transvaginal ultrasound and whether cervical defects can be identified if performed by direct care team for clinically indicated reasons at any point.
5. Identify women who require referral into specialist preterm surveillance clinics.
6. Identify potential participants for CRAFT-RCT (see Figure 1).

CRAFT-RCT: a trial of USS indicated cerclage in women with history of FDCS

The aim of this trial is to evaluate efficacy of cervical cerclage in pregnant women with a short cervix ($\leq 25\text{mm}$) on TVS between 14⁺⁰ and 23⁺⁶ weeks gestation following a FDCS. The study will allow us to evaluate the impact of cervical cerclage on:

1. Primary obstetric outcome – spontaneous preterm birth rate < 34 weeks gestation.
2. Secondary outcomes - Short-term pregnancy and neonatal outcomes, including a composite of neonatal death and morbidity.

CRAFT-IMG: a study evaluating imaging methods for assessing risk and management of women with a history of FDCS

This imaging sub-study will focus on analysis of TVS and magnetic resonance imaging (MRI) of cervical defects in this population to elucidate which women are at increased risk of PTB/LM. Assessment of any identified cervical defect and its relation to a cervical cerclage will also help us to establish which women at risk of PTB would benefit from this treatment.

Objectives of the imaging study:

1. To assess whether cervical abnormalities can be visualised in the cervix by TVS and MRI.

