4.2. CRAFT-RCT

Primary endpoint:

- i. Delivery <34 weeks gestation (powered)

Secondary endpoints:

- i. Adverse perinatal outcome, defined as composite outcome of death (ante-partum/intra-partum stillbirths plus neonatal deaths prior to discharge from neonatal services) or one/more of intraventricular haemorrhage, periventricular leukomalacia, hypoxic ischaemic encephalopathy, necrotizing enterocolitis, bronchopulmonary dysplasia and sepsis.
- ii. Gestation at delivery.
- iii. Requirement for rescue cerclage (bulging fetal membranes).
- iv. Time between intervention and delivery.
- v. Health costs at 28 days post-delivery.

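### The neonatal follow-up rule in section 7.3 (sooner of discharge or 28 days) conflicts with the death horizon in 4.1(i) and 4.2(i) and with the 28-day cost endpoint in 4.2(v)

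*Combined protocol and SAP*

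**What the plan says.** **Follow-up rule.** Section 7.3 (Data Collection, outcome data): "Neonates will be followed up until discharge or 28 days (whichever is sooner"). Women's data are collated to postnatal discharge, a term that neither 7.3 nor 3.4 defines. The same paragraph ends by saying that primary and secondary outcomes are taken from hospital records after the baby has left neonatal care, with no 28-day limit.

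**Death and morbidity.** Section 4.1(i), for CRAFT-OBS, is "defined as a composite outcome of death (ante-partum/intra-partum stillbirths plus neonatal deaths prior to discharge from neonatal services"). Section 4.2(i), for CRAFT-RCT, uses the same words for deaths, "neonatal deaths prior to discharge from neonatal services", and adds "or one/more of intraventricular haemorrhage, periventricular leukomalacia, hypoxic ischaemic encephalopathy, necrotizing enterocolitis, bronchopulmonary dysplasia and sepsis". No assessment time is given for these six morbidities.

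**Costs.** Section 4.2(v), for CRAFT-RCT only: "Health costs at 28 days post-delivery". The matching objective, 2.2.2(ii), refers to "health economic outcomes for mother and infant in terms of number of nights in hospital; cost data to hospital discharge/28 days post delivery".

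**End of study.** Section 3.4 uses the same sooner-of-two-dates rule, applied to the last recruited participant and her infant.

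Section 8 (Data analysis) refers back to the endpoints in 4.2 and gives no time window of its own.

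**The concern.** A follow-up window has to be at least as long as the endpoints that depend on it. A rule that takes the earlier of two dates will fall short of an endpoint defined by either date alone whenever the other date comes first. Here one endpoint is defined by discharge and another by day 28, so the rule appears to fall short of one or the other for nearly every baby.

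CRAFT-RCT is planned in at least 41 hospitals (section 3.2). A site that follows the sooner-date sentence closes the record of a long-stay baby at day 28. A site that follows the last sentence of the same paragraph waits until the baby leaves neonatal care. The same secondary endpoint could then be collected over different windows. For costs, a site that stops at discharge would supply cost to discharge under an endpoint labelled as cost at 28 days.

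**Working it through.** **1. The plan's own figure.** The only nearby figure that can be reproduced is the RCT sample size in section 5: 10% versus 5%, 80% power, 474 per group. A two-sided 5% level is assumed, since none is stated.

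- Without continuity correction: n = [1.960·√(2·0.075·0.925) + 0.842·√(0.10·0.90 + 0.05·0.95)]² / 0.05² = (0.730 + 0.312)² / 0.0025, which rounds up to 435.
- With continuity correction: (n/4)·[1 + √(1 + 4/(n·0.05))]² gives 474, as stated.
- With 5% loss: 474/0.95 = 498.9, so 499, rounded in the plan to 500.

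This calculation concerns delivery before 34 weeks, which is fixed at birth. Nothing below changes it.

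**2. Comparing the windows.** Let D be the day of discharge, taking discharge in 7.3 to be discharge from neonatal services (an assumption for babies admitted there).

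- Follow-up under the sooner-date sentence of 7.3: min(D, 28).
- Death horizon in 4.1(i) and 4.2(i): D.
- Cost horizon in 4.2(v): 28.

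Shortfall for deaths = D − min(D, 28). Shortfall for costs = 28 − min(D, 28). The values of D below are illustrative, because the documents give no lengths of stay.

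| D (days) | Follow-up ends | Short of death horizon | Short of cost horizon |
|---|---|---|---|
| 2 | 2 | 0 | 26 |
| 14 | 14 | 0 | 14 |
| 28 | 28 | 0 | 0 |
| 45 | 28 | 17 | 0 |
| 60 | 28 | 32 | 0 |

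Only D = 28 satisfies both endpoints. A baby born at 24+0 weeks reaches day 28 at 28+0, and one born at 28+0 reaches it at 32+0.

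**3. Does another passage settle the horizon?**

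- *Deaths.* If neonatal were defined as the first 28 days, 4.1(i) and 4.2(i) would carry an implicit cap and the first shortfall would vanish. The documents give no such definition.
- *Costs.* Objective 2.2.2(ii) names both dates separated by a slash and does not say which governs. It covers mother and infant, while 3.4 and 7.3 stop the mother's data at postnatal discharge. Section 7.3 takes economic data from NHS records and tracks admissions, but gives no end date for either.
- *End of study.* Section 3.4 is not a rule for each baby. Read literally, it could close the study while the last infant is still in neonatal care.

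**The case against.** The best defence is in 7.3 itself. Its closing sentence is specific to primary and secondary outcomes and has them collected once the baby has left neonatal care, which fits 4.1(i) and 4.2(i). The paragraph also provides for contacting the patient, her GP or another hospital when information is missing, and mother and baby NHS numbers are held (7.2, 10.3). Section 9.5.2 runs adverse-event recording to 28 days after delivery, and 9.5.3 sends outcome events to the case report form, so exemption from SAE reporting does not mean an event goes unrecorded. On costs, 2.2.2(ii), 3.4 and 7.3 all pair the same two dates. It is plausible that cost to the sooner date was intended throughout, with 4.2(v) as a short form.

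Much of this stands. Many late deaths and readmissions may well be captured in practice, and the intended cost horizon is open. It does not remove the conflict. Two sentences in one paragraph give different stopping points, and no passage says which prevails. If cost to the sooner date is meant, 4.2(v) is worded wrongly and still needs correction.

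A reader might infer that late deaths will be lost, or that the treatment comparison on the composite is biased. The documents support neither: they provide a route to capture, and they give no composite rate, length of stay or share of late events. A reader might also try to cap the number of babies affected with the planning rates (500 × 10% + 500 × 5% = 75 births before 34 weeks). That is not a ceiling. Section 5 gives 10% as a minimum, for births after full-dilatation caesarean generally and not for the short-cervix women in the RCT. Nor do the documents say that long stays arise only from births before 34 weeks.

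**Conclusion.** The conflict is real and follows from the literal text. The sooner-date sentence of 7.3 ends before the death horizon of 4.1(i) and 4.2(i) for babies in neonatal care beyond day 28, and before the cost horizon of 4.2(v) for babies discharged earlier. It also disagrees with the closing outcome sentence of its own paragraph. The mother's window has the same problem for costs whenever postnatal discharge comes before day 28. The death part assumes that neonatal is not meant as the first 28 days. The cost part assumes that 4.2(v) means what it says.

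The consequence is possible variation in collection windows between sites, not a demonstrated loss of data. Only secondary endpoints are affected: the composite in both studies and costs in CRAFT-RCT. CRAFT-OBS has no 28-day cost endpoint. The primary endpoints (delivery before 37 and before 34 weeks) and the 474 per group are unaffected. The number of events or costs that might be missed cannot be derived from the documents, so no shift in an odds ratio, risk difference or NNT is claimed.

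**What to change.** In 7.3, replace the single sooner-date rule with one horizon per endpoint.

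- **Composite, 4.1(i) and 4.2(i).** Collect deaths and, for the RCT, the six morbidities to discharge from neonatal services, as both sections already word it for deaths. State whether a death after day 28 but before discharge counts.
- **RCT costs, 4.2(v) and 2.2.2(ii).** Choose one horizon and apply it to all mothers and babies. Either follow records to day 28, as 4.2(v) states, and name the source of data between discharge and day 28; or reword both sections as cost to the sooner date, if that is what is meant.
- **End of study, 3.4.** Word it so that the study does not end before the last infant's horizon.

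The cost is a text amendment, later reading of long-stay records and a slightly later close. If the 28-day cost horizon is kept, records of RCT mothers and babies discharged earlier must also be checked to day 28. Outcomes already come from NHS records and NHS numbers are already collected, so no new data system is needed. The second cost option avoids the additional checks, but yields cost over a period that varies with length of stay.
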